9.7.3 Determination of Sample Size

Sample size estimates were based on a pilot trial of heparin-lidocaine versus lidocaine alone and a prior two-arm study of URG101 versus placebo. The primary efficacy endpoint is SPID-12. The sample size calculation is based on a one-way analysis of variance, comparing SPID-12 from four treatment groups. A target sample size of approximately 180 subjects allocated among the four treatment groups. This sample size will be sufficient to achieve 90% power to detect a difference between the URG101 and components groups assuming a treatment effect size of 0.60. Once 50% of the subjects (90) have been enrolled, an unblinded interim assessment will be performed. The number of subjects for the study may be increased, based on the recommendation of the IDMC. Overall, a maximum of 300 subjects will be enrolled in Study URG101-105.

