Statistical Methods:	
Sample Size Estimate Sample size estimates were based on a pilot trial of heparin-lidocaine versus lidocaine alone and a prior two-arm study of URG101 versus placebo. The primary efficacy endpoint is SPID-12. The sample size calculation is based on a one-way analysis of variance, comparing SPID-12 from four treatment groups. A target sample size of 180 subjects to be allocated unequally among the four treatment groups as follows: URG101:placebo:lidocaine: heparin at 2:1:2:1 (60 subjects per group and 30 subjects per group). This sample size is sufficient to achieve 90% power to detect a difference between the URG101 and lidocaine groups assuming a treatment effect size of 0.60. The study will also have 90% power to detect a difference between the URG101 and each of the placebo and heparin groups assuming an effect size for these comparisons of 0.75. Once 90 subjects have been enrolled, a blinded interim analysis will take place; and, if required, the number of subjects for the study increased to a maximum of 300 subjects.
 
Description of Analysis Sets: All analyses of the efficacy of URG101 will be performed on the ITT set, which will include all randomized subjects from the investigative phase of the study who receive study drug. These efficacy analyses will compare the treatment groups on the basis of randomized treatment, regardless of the treatment actually received. Primary efficacy and key secondary efficacy analyses will also be conducted on a per protocol set, which will include all subjects in the ITT set who sufficiently comply with the protocol.
 
Safety analyses will be based on the safety analysis set which will include all subjects who receive at least one dose of study drug and have at least one post dose safety assessment in both phases of the study. Safety summaries will be produced based on study treatment actually received.

CLINICAL PROTOCOL SYNOPSIS (continued)

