9.7.1 Statistical and Analytical Plans

The statistical analyses of study data are described in this section. All hypothesis tests will be 2-sided and will use an alpha level of 0.05. Additional details of the analytical plan will be provided in the SAP, which will be finalized before database lock.

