9.7.1.14 Efficacy Analyses

All SPID endpoints will be calculated using Simpson's trapezoidal rule. SPID will be calculated as follows, where n is the total number of time points within the time period with non-missing imputed PID values:

If multiple scores are recorded at the same date and time, the most conservative PI scores (highest) will be used.

Primary Efficacy Analyses

The primary efficacy analyses will be performed on the intent-to-treat set. As a sensitivity analysis, the primary efficacy analysis will also be performed on the PP set. Primary efficacy analyses will also be conducted on the per protocol set, which will include all subjects in the ITT set who sufficiently comply with the protocol.

The primary efficacy endpoint will be compared between the URG101 group and the lidocaine, heparin, and placebo groups using an analysis of covariance model including factors for site and randomized treatment assignment; baseline pain will be added to the model as a covariate. Pairwise comparisons of least squares means between URG 101 and the two active treatment arms, as well as the placebo arm, will be performed. The probability values will be derived using the contrast statement from the model. If the p-value associated with these comparisons is < 0.05 in favor of URG101, the primary aim of the trial will be confirmed.

Sites with small numbers of patients enrolled may be pooled for analysis. The method used to determine pooling will be specified in the statistical analysis plan and any pooling will be finalized and documented prior to database lock and unblinding.

Secondary Efficacy Analyses

Analyses of the secondary endpoints relating to changes in the pain and urgency NRS will be performed using analysis of covariance models similar to those used for the primary efficacy endpoint. The ITT set will be used. Nonparametric methodology in exploratory analyses may be used to supplement the parametric analyses.

Treatment differences based on the PORIS questionnaire, Question 3, will be analyzed by pairwise Cochran-Mantel-Haenszel Tests based on $\geq 50\%$ improvement of symptoms.

Time to first pain medication use will be analyzed using Kaplan-Meier methodolgy. Log-rank tests will be used to compare the treament groups.

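### Section 9.7.3 claims 90% power against both components at effect size 0.60; for heparin (60 vs 30) a pairwise test has about 76%, and the synopsis assumes 0.75 there

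*Combined protocol and SAP*

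**What the plan says.** Section 9.7.3 bases the calculation on a one-way analysis of variance of SPID-12 in four groups. It gives a total of about 180 and claims "90% power to detect a difference between the URG101 and components groups assuming a treatment effect size of 0.60". It states no arm sizes, no second effect size and no power against placebo. Section 9.1 identifies the individual components as heparin and lidocaine.

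The synopsis (Section 2.0, Sample Size Estimate) uses the same total and the same analysis-of-variance basis but splits the claim. For lidocaine, the sample is "sufficient to achieve 90% power to detect a difference between the URG101 and lidocaine groups assuming a treatment effect size of 0.60". For the other two comparators, it has 90% power for "each of the placebo and heparin groups assuming an effect size for these comparisons of 0.75". Allocation is 2:1:2:1 for URG101, placebo, lidocaine and heparin, which the synopsis writes as "60 subjects per group and 30 subjects per group".

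On the deciding test, Section 9.7.1.14 says: "Pairwise comparisons of least squares means between URG 101 and the two active treatment arms, as well as the placebo arm, will be performed". Section 9.7.1 adds: "All hypothesis tests will be 2-sided and will use an alpha level of 0.05".

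**The concern.** Both sections are current text, and they disagree on the effect assumed for URG101 versus heparin: 0.60 in Section 9.7.3 and 0.75 in the synopsis. Heparin has half as many subjects as lidocaine, so one effect size cannot give the same power for both at these arm sizes.

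URG101 versus heparin is one of the contrasts in the primary analysis, and Section 9.2 presents the contribution of the components as the reason for the four-arm design. Someone relying on Section 9.7.3 would put the type II error for heparin at 0.60 at 10%, when it is about 24% (100% minus 76%). They would also believe the trial was sized for a smaller heparin effect than the synopsis assumes.

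**Working it through.** **Inputs.** Arms: URG101 60, placebo 30, lidocaine 60, heparin 30 (synopsis). Two-sided alpha 0.05 (Section 9.7.1), with no split across comparisons. Effect sizes 0.60 and 0.75 (synopsis; 0.60 only in Section 9.7.3). Deciding test: pairwise contrasts (Section 9.7.1.14). Effect size d is read as a standardised mean difference (SD = 1), with no covariate gain at first.

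**Formula.** Noncentrality = d / sqrt(1/n1 + 1/n2). Power comes from the noncentral t with n1 + n2 − 2 df, or 176 df if the error variance is pooled over four arms (180 − 4). The normal approximation is Φ(noncentrality − 1.960).

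**The plan's figures first.**

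| Comparison | n | d | Noncentrality | Normal | t (two-arm df) | t (176 df) |
|---|---|---|---|---|---|---|
| Lidocaine (synopsis and 9.7.3) | 60 vs 60 | 0.60 | 0.60/0.1826 = 3.286 | 90.8% | 90.3% | 90.5% |
| Heparin or placebo (synopsis) | 60 vs 30 | 0.75 | 0.75/0.2236 = 3.354 | 91.8% | 91.3% | 91.6% |
| Heparin (9.7.3) | 60 vs 30 | 0.60 | 0.60/0.2236 = 2.683 | 76.5% | 75.6% | 76.1% |

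The first two rows reproduce the stated 90%. The third does not.

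**Effect needed for 90% at 60 vs 30.** Normal: (1.960 + 1.282) × 0.2236 = 0.725. Noncentral t: 0.733 (88 df) or 0.729 (176 df).

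**Other readings tried for heparin at 0.60.**

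- One-sided 0.05: about 85%.
- Equal arms of 45: 80% to 81%.
- Bonferroni: 66% over two tests, 61% over three.
- Both components pooled, 60 vs 90: 94.7% (t) or 95.0% (normal).
- Omnibus four-group F test with URG101 0.60 above three equal comparators: grand mean 60 × 0.60/180 = 0.20; λ = 60 × 0.40² + 120 × 0.20² = 9.6 + 4.8 = 14.4; df 3 and 176; power 89.8%.

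**Covariate gain.** The documents give no correlation between baseline pain and SPID-12, so any value is an assumption. If 0.60 is on the unadjusted SD, replace d by 0.60/sqrt(1 − ρ²), with 175 df and no allowance for the site factor. Power for heparin is then 79.9% at ρ = 0.3, 82.9% at 0.4 and 86.9% at 0.5. Reaching 90% needs ρ of about 0.57.

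**The case against.** The strongest defence is that Section 9.7.3 names a one-way analysis of variance, and the omnibus F test at 0.60 gives 89.8%, which rounds to the stated figure. If the components are taken together, 60 vs 90 also exceeds 90%. On this view the sentence is ambiguous, not miscalculated, and it is probably a shortened copy of the synopsis that lost a clause.

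The explanation of how the sentence arose is plausible, but neither reading rescues it. The synopsis cites the same analysis of variance and then states power per comparison. The omnibus scenario puts heparin and placebo at 0.60, against 0.75 in the synopsis. The primary aim is decided by pairwise contrasts, and no pooled-component test is planned.

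Two further points stand. First, the 76% is conditional: the primary model adjusts for baseline pain, and the documents do not say which SD the effect size uses, so the covariate range belongs beside it. Second, if the primary aim needs all three contrasts to succeed, per-comparison power is not the power of the decision rule. Under the synopsis effects, simulation without covariate gain gives about 79% for all three and about 84% for lidocaine and heparin together. That is a separate matter and does not make power figures labelled per comparison incorrect.

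At the maximum of 300 subjects (100 vs 50), power for heparin at 0.60 would be about 93%, but the sentence concerns the planned 180.

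**Conclusion.** The concern holds. As written, Section 9.7.3 is wrong for URG101 versus heparin: about 76% power at 0.60, not 90%, for a two-sided 0.05 pairwise test of 60 vs 30 without covariate gain. Plausible covariate gain narrows the gap but closes it only at an assumed correlation of about 0.57. Section 9.7.3 and the synopsis also contradict each other on the planning effect for this comparison.

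The consequence is limited. The synopsis figures are internally sound, and on those assumptions each comparison has at least 90% power with 180 subjects. Nothing here bears on the interim decision.

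**What to change.** Reconcile Section 9.7.3 with the synopsis by stating arm sizes, effect size and power for each comparison: URG101 vs lidocaine, 60 vs 60, effect size 0.60, 90%; URG101 vs heparin and URG101 vs placebo, 60 vs 30 each, effect size 0.75, about 91%. Label these as power per pairwise comparison at two-sided 0.05, and say whether the effect size is on the unadjusted or the covariate-adjusted SD.

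If 0.60 is really intended for heparin, state the power as about 76% with no covariate gain assumed, and correct the synopsis to match. Keeping 90% at 0.60 under 2:1:2:1 allocation would instead need 44 heparin subjects by the normal approximation (44 × 6 = 264 in total) or 45 by the t calculation (45 × 6 = 270).

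Aligning with the synopsis costs one or two sentences and changes neither the sample size of 180, the analysis nor the conduct of the trial.

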9.7.4 Interim Analysis

Re-estimation of the Sample Size

The two possible types of interactions are defined as being either **quantitative** or **qualitative**. A quantitative interaction exists where the relationship of the treatment groups are consistent across the sites, moving in the same direction, but at different magnitudes. A qualitative interaction is much more serious and exists where one treatment group shows a positive effect of the study medication at certain sites, and the other sites show a negative effect of the same study treatment. In most clinical studies, if an interaction is present between site and treatment, there will be a quantitative interaction where the effect size at some sites is greater than at other

sites, but all sites have a positive effect size for the active treatment. Qualitative interactions require additional investigation because of the mixed signals on the effect of a study treatment by study site.

In order to minimize the impact of a small sample effect, for the purposes of the interim analysis, the smaller study sites will be merged to form a pseudo-site. In this way a possible aberration in outcomes that might arise from small samples due to over or under representation of patients with characteristics that may either increase or decrease study results will have a diminished impact on the sample size recalculation.

[figure not shown]

10

2

[REDACTED] : [REDACTED] : [REDACTED]

W

The IDMC will make one of following non-binding recommendations to the sponsor:

- Continue enrolling patients to the pre-specified target sample size
- Continue enrolling patients to a sample size that exceeds the pre-specified target sample size but \leq the maximum sample size
- Stop enrolling patients based on futility

The instructions from the IDMC for the sample size adjustment will be described in detail in the IDMC Charter. An alpha level adjustment will not be necessary for the

procedure described below if the conditional power for the primary endpoint is > 39%.

9.7.5 Other Statistical and Analytical Issues

Not applicable.

9.7.6 Procedure for Revising the Statistical Analysis Plan

If the SAP requires revision after finalization, the sponsor will determine how the revision impacts the study and how the revision should be implemented. The details of the revision will be documented and described in the clinical study report.

10.0 ADMINISTRATIVE PROCEDURES AND INSTRUCTIONS

10.1 CHANGES TO THE PROTOCOL

Any change to the protocol requires a written protocol amendment or administrative change that must be approved by the investigator, IRB, and Urgen before implementation. Amendments specifically affecting the safety of subjects, the scope of the investigation, or the scientific quality of the study require submission to health or regulatory authorities as well as additional approval by the applicable IRBs. These requirements should in no way prevent any immediate action from being taken by the investigator, in the interest of preserving the safety of all subjects included in the study. If the investigator determines that an immediate change to or deviation from the protocol is necessary for safety reasons to eliminate an immediate hazard to the subjects, Urgen and the IRB for the site must be notified immediately. The sponsor must notify the health or regulatory authority as required per local regulations.

Protocol amendments that affect only administrative aspects of the study may not require submission to health or regulatory authority or the IRB, but the health or regulatory authority and IRB should be kept informed of such changes as required by local regulations. In these cases, the sponsor may be required to send a letter to the IRB detailing such changes.

10.2 ADHERENCE TO THE PROTOCOL

The investigator will conduct the study in strict accordance with the protocol (refer to ICH E6, Section 4.5).

10.3 MONITORING PROCEDURES

The sponsor's contract research organization or clinical research associate (CRA) will maintain contact with the investigator and designated staff by telephone, letter, or email between study visits. Monitoring visits to each site will be conducted by the assigned CRA as described in the monitoring plan. The investigator, or if regionally required, the head of the medical institution will allow the CRA to inspect the clinical, laboratory, and pharmacy facilities to assure compliance with GCP and local regulatory requirements. The CRFs and subject's corresponding original medical records (source documents) are to be fully available for review by the sponsor's

representatives at regular intervals. These reviews verify adherence to study protocol and data accuracy in accordance with local regulations. All records at the site are subject to inspection by the local auditing agency and IRB or IEC review.

In accordance with ICH E6, Section 1.52, source documents include, but are not limited to the following:

- Clinic, office, or hospital charts
- Copies or transcribed health care provider notes which have been certified for accuracy after production
- Recorded data from automated instruments such as IxRS, x-rays, and other imaging reports (e.g., sonograms, computed tomography scans, magnetic resonance images, radioactive images, ECGs, rhythm strips, polysomnographs, pulmonary function tests), regardless of how these images are stored, including microfiche and photographic negatives
- Pain, quality-of-life, or medical history questionnaires completed by subjects
- Records of telephone contacts
- Diaries or evaluation checklists
- Drug distribution and accountability logs maintained in pharmacies or by research personnel
- Laboratory results and other laboratory test outputs (e.g., urine pregnancy test result documentation and urine dip-sticks)
- Correspondence regarding a study subject's treatment between physicians or memoranda sent to the IRBs
- CRF components (e.g., questionnaires) that are completed directly by subjects and serve as their own source

10.4 RECORDING OF DATA

A CRF is required and must be completed for each subject by qualified and authorized personnel. All data on the CRF must reflect the corresponding source document, except when a section of the CRF itself is used as the source document. Any correction to entries made on the CRF must be documented in a valid audit trail where the correction is dated, the individual making the correction is identified, the reason for the change is stated, and the original data are not obscured. Only data required by the protocol for the purposes of the study should be collected.

The investigator must sign each CRF.

10.5 IDENTIFICATION OF SOURCE DATA

All data to be recorded on the CRF must reflect the corresponding source documents.

10.6 RETENTION OF RECORDS

The circumstances of completion or termination of the study notwithstanding, the investigator is responsible for retaining all study documents, including but not limited to the protocol, copies of CRFs, the Investigator's Brochure, and regulatory agency registration documents (e.g., Form FDA 1572, ICFs, and IRB correspondence). The site should plan to retain study documents for the length of time agreed upon in the study contract.

It is requested that at the completion of the required retention period, or should the investigator retire or relocate, the investigator contact Urigen, allowing Urigen the option of permanently retaining the study records.

10.7 AUDITING PROCEDURES AND INSPECTION

In addition to the routine monitoring procedures, the Urigen Clinical Quality Assurance department conducts audits of clinical research activities in accordance with Urigen's procedures to evaluate compliance with the principles of ICH GCP and all applicable local regulations. If a government regulatory authority requests an inspection during the study or after its completion, the investigator must inform Urigen immediately.

10.8 REPORTING AND PUBLICATION OF RESULTS

A clinical study report will be finalized within 1 year of the end of data collection.

All manuscripts, abstracts, or other modes of presentation arising from the results of the study must be reviewed and approved in writing by Urigen in advance of submission pursuant to the terms and conditions set forth in the executed Clinical Study Agreement between Urigen and the institution or investigator. The review is aimed at protecting Urigen's proprietary information existing either at the date of the commencement of the study or generated during the study.

The detailed obligations regarding the publication of any data, material results, or other information, generated or created in relation to the study, will be set out in the agreement between the investigator and Urigen, as appropriate.

10.9 DISCLOSURE AND CONFIDENTIALITY

The contents of this protocol and any amendments and results obtained during the study should be kept confidential by the investigator, the investigator's staff, and the IRB and will not be disclosed in whole or in part to others, or used for any purpose other than reviewing or performing the study, without the written consent of Urigen. No data collected as part of this study will be used in any written work, including publications, without the written consent of Urigen. These obligations of confidentiality and nonuse will in no way diminish such obligations as set forth in either the Confidentiality Agreement or Clinical Study Agreement executed between Urigen and the institution or investigator.

All persons assisting in the performance of this study must be bound by the obligations of confidentiality and nonuse set forth in either the Confidentiality Agreement or Clinical Study Agreement executed between the institution or investigator and Urigen.

10.10 DISCONTINUATION OF STUDY

Urigen reserves the right to discontinue the study for medical reasons or any other reason at any time. If a study is prematurely terminated or suspended, Urigen will promptly inform the investigators or institutions and the investigator will inform the

regulatory authorities of the termination or suspension and the reason(s) for the termination or suspension. The IRB will also be informed promptly and provided the reason(s) for the termination or suspension by the investigator or institution, as specified by the applicable regulatory requirement(s).

The investigator reserves the right to discontinue the study if his or her judgment so dictates. If the investigator terminates or suspends a study without prior agreement of Urgen, the investigator should inform the institution where applicable, and the investigator or institution should promptly inform Urgen and the IRB and provide Urgen and the IRB with a detailed written explanation of the termination or suspension. Study records must be retained as noted above.

Appendix 6 Guideline Script for Patient Overall Rating of Improvement of Symptoms Questionnaire

Appendix 7 Protocol Signature Pages

Appendix 1: Pelvic Pain and Urgency/Frequency Questionnaire

PELVIC PAIN and URGENCY/FREQUENCY SCALE

Please circle the answer that best describes how you feel for each question.

	0	1	2	3	4	Symptom Score	Bother Score
1 How many times do you go to the bathroom during the day?	3-6	7-10	11-14	15-19	20+		
2 a. How many times do you go to the bathroom at night?	0	1	2	3	4+		
b. If you get up at night to go to the bathroom, does it bother you?	Never Bothers	Occasionally	Usually	Always			
3 a. Do you now or have you ever had pain or symptoms during or after sexual intercourse?	Never	Occasionally	Usually	Always			
b. Has pain or urgency ever made you avoid sexual intercourse?	Never	Occasionally	Usually	Always			
4 Do you have pain associated with your bladder or in your pelvis (vagina, labia, lower abdomen, urethra, perineum, testes, or scrotum)?	Never	Occasionally	Usually	Always			
5 a. If you have pain, is it usually		Mild	Moderate	Severe			
b. Does your pain bother you?	Never	Occasionally	Usually	Always			
6 Do you still have urgency after going to the bathroom?	Never	Occasionally	Usually	Always			
7 a. If you have urgency, is it usually		Mild	Moderate	Severe			
b. Does your urgency bother you?	Never	Occasionally	Usually	Always			
8 Are you sexually active? Yes ____ No ____							

SYMPTOM SCORE = (Add scores from top of column: 1, 2a, 3a, 4, 5a, 6, 7a)	
BOTHER SCORE = (Add scores from top of column: 2b, 3b, 5b, 7b)	
TOTAL SCORE (Symptom Score + Bother Score) =	

Appendix 2: Guideline Script for Pelvic Pain and Urgency/Frequency Questionnaire**Guideline script:**

[REDACTED]

[REDACTED]

[REDACTED]

[REDACTED]

[REDACTED]

[REDACTED]

[REDACTED]

[figure not shown]
[REDACTED]

.....

[figure not shown]
Once the subject has answered all questions the coordinator will enter the scores (0, 1, 2, 3, or 4 as indicated at the top of the page) to the right, and then calculate the total SYMPTOM SCORE, total BOTHER SCORE, and TOTAL SCORE (Symptom score + Bother Score).

